10.3.6 Vital signs and physical examination

Patient's vital signs (pulse rate, respiration rate, systolic blood pressure, diastolic blood pressure and temperature) will be presented as follows:

For each timepoint (baseline, weeks 4, 12, 24, 36 and 48, and the safety follow-up visit) absolute values and change from baseline will be summarized with standard summary statistics (see Section 8.1), by

REACH TRIAL

treatment group. Weight will be presented in a similar way, but only at baseline, weeks 24 and 48, and the safety follow-up visit.

An on-treatment summary of vital signs will be presented. A low category and one or two high categories are pre-specified as follows:

Vital Signs Parameter	Low category	High Categories
Systolic blood pressure (mmHg)	< 90	> 140 to \leq 160 > 160
Diastolic blood pressure (mmHg)	< 50	> 90 to \leq 100 > 100
Pulse rate (bpm)	< 60	> 100
Temperature (°C)	< 36.0	> 38.0
Respiratory rate (breaths/min)	< 12	> 20
Body weight	\geq 7% decrease from baseline while on-treatment	\geq 7% increase from baseline

For each measurement type the number and percentage of patients: in each category at baseline (except body weight); with minimum on-treatment measurement in the lowest category; and with maximum on-treatment measurement in the highest category/categories will be presented.

All vital signs data will be presented by patient in a listing, by FSHD type and treatment group.

All physical examination data will be presented by patient in a listing, by FSHD type and treatment group.

10.3.7 Electrocardiogram (ECG)

Each patient's maximum on-treatment QTcF interval will be categorized as \leq 450, > 450 to \leq 480, > 480 to \leq 500, > 500. The number and percentage of patients in each category will be presented by treatment group. Each patient's maximum on-treatment change from baseline in QTcF interval will be categorized as < 0, \geq 0 to \leq 30, > 30 to \leq 60, > 60. The number and percentage of patients in each category will be presented by treatment group.

All ECG data will be presented by patient in a listing, by FSHD type and treatment group

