1.3.5.2. Thorough QT Study

A thorough QT study (PM1116628) was conducted with losmapimod at 7.5 mg BID or 20 mg once daily or placebo administered for 5 days in healthy volunteers. Moxifloxacin (single 400 mg dose) was included as a positive control. The primary PD analysis showed that, at the 20 mg dose of losmapimod, the upper bound of the 90% CI of $\Delta\Delta QTcF$ (change from baseline in QT interval corrected for heart rate by Fridericia's formula [QTcF] compared to that for placebo) exceeded the 10 msec threshold at the 24-hour post-dose time point. For the 7.5 mg dose, the upper bound of the 90% CI of $\Delta\Delta QTcF$ exceeded the 10 msec threshold at multiple time points. No subjects experienced QTcF values >480 msec or QTcF changes from baseline ≥ 60 msec at any time in the study. PK/PD modeling, using the raw QTcF and plasma concentration data, showed that at plasma losmapimod concentrations 4 times the 7.5 mg BID exposure, ie, at exposures approximately 2-fold higher than 15 mg BID, the predicted upper bound of the 90% CI of $\Delta\Delta QTcF$ did not exceed 10 msec and the predicted median $\Delta\Delta QTcF$ was less than 5 msec.

In summary, although the upper bound of the 90% CI exceeded the 10 msec regulatory threshold of concern in the primary PD analysis, it is unlikely that there will be a clinically relevant effect on the QT interval data, as there was no clinically relevant concentration QTc effect using standard placebo/baseline subtracted measured QTc data. Additional information on the QTc interval and its behavior as demonstrated in the large cohort of patients treated with losmapimod obtained from Study PM1116197 supports the lack of a QT effect.

Across the completed and ongoing Fulcrum losmapimod studies, there were no notable or clinically meaningful changes or trends noted in changes from baseline in ECG parameters; this was confirmed by ECG interpretation by visit.

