- Positive for hepatitis C antibody unless additional testing for hepatitis C viral RNA is negative, ALT is $< 2 \times$ ULN and total bilirubin is $\leq 1.5 \times$ ULN, indicating inactive/resolved hepatitis C infection.

8. Known severe renal impairment (defined as a glomerular filtration rate of < 30 mL/min/1.73 m²).
9. Standard 12-lead ECG demonstrating QTcF >450 msec for male patients and QTcF >470 msec for female patients at screening. If QTcF exceeds 450 msec for males or 470 msec for females, the ECG will be repeated 2 more times, and the average of the 3 QTcF values will be used to determine the patient's eligibility.
10. History of cardiac dysrhythmias requiring anti-arrhythmia treatment(s); or history or evidence of abnormal ECGs that, in the opinion of the Investigator or Medical Monitor, would preclude the patient's participation in the study.
11. Male patients with a female partner who is planning to become pregnant during the study or within 90 days after the last study drug dose.
12. Concomitant use of cytotoxic chemotherapy for cancer or known ongoing or anticipated use of chronic severe immunosuppressive agents.
13. Positive pregnancy test, known to be pregnant or lactating, or planning to become pregnant during study drug administration and until 90 days after last dose.
14. Any current mental condition (psychiatric disorder, senility or dementia) that may affect study compliance or prevent understanding of the aims, investigational procedures, or possible consequences of the study.
15. Patient has any condition possibly affecting drug absorption (eg, gastrectomy, cholecystectomy, or other gastrointestinal tract surgery, except appendectomy).
16. History of alcohol, analgesic/opioid, and/or illicit drug abuse, as defined by the Diagnostic and Statistical Manual of Mental Disorders, Fifth Edition (American Psychiatric Association, 2013), in the last 6 months before screening or a positive test for drugs of abuse at screening. Use of CBD/THC is permitted.
17. Use of another investigational product within 30 days or 5 half-lives (whichever is longer) or according to local regulations, or currently participating in a study of an investigational device.
18. Current or anticipated participation in a natural history study. Previous participation is allowed but patients cannot continue after enrollment in Study 1821-FSH-301.
19. Known hypersensitivity or intolerance to losmapimod or any of its excipients.

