9.1.6.7. Safety Analyses

Safety data in the placebo-controlled treatment period will be analyzed using the safety analysis set and summarized by treatment group and visit (if applicable) using descriptive statistics.

Treatment-emergent AEs will be summarized by MedDRA system organ class and preferred term; separate summaries will be produced for treatment-related AEs, AESIs, SAEs, and discontinuations due to AEs. Laboratory tests, vital signs, findings from physical examinations, and ECGs will be summarized for changes over time during treatment using descriptive statistics.

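### SAP 10.3.7 gives QTcF only as categories of maximum value and maximum change; the ECG summary over time in protocol 9.1.6.7 is missing, and SAP 11 does not declare this

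*SAP*

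**What the plan says.** **Protocol 9.1.6.7 (Safety Analyses, Part A).** Safety data are to be "summarized by treatment group and visit (if applicable) using descriptive statistics". The next paragraph adds: "Laboratory tests, vital signs, findings from physical examinations, and ECGs will be summarized for changes over time during treatment using descriptive statistics".

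**SAP 10.3.7 (ECG)** specifies three outputs:
- Each patient's "maximum on-treatment QTcF interval will be categorized as" up to 450, above 450 to 480, above 480 to 500, or above 500.
- Each patient's "maximum on-treatment change from baseline in QTcF interval will be categorized as" below 0, 0 to 30, above 30 to 60, or above 60.
- A listing: "All ECG data will be presented by patient in a listing, by FSHD type and treatment group".

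**SAP 10.3.5 and 10.3.6 (laboratory tests, vital signs)** ask for values and change from baseline at baseline, Weeks 4, 12, 24, 36 and 48, and safety follow-up. SAP 10.3.6 also asks for baseline category counts for every vital sign except body weight.

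**SAP 11** declares no changes from the protocol-specified analysis. **SAP Appendix A** points to a separate file of table shells that is not among the documents.

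**The concern.** ECGs are a named component of the secondary safety endpoint (protocol 2.1.2, SAP 2.3.2). A maximum taken across visits discards the visit, so neither planned table shows change over time. No ECG parameter other than QTcF is tabulated. The maximum of several single ECGs also picks up measurement noise in both arms, which blurs a small average shift.

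The maximum-QTcF table is hard to read without baseline counts. The exclusion criterion for women is "QTcF >470 msec for female patients at screening", so women at 451 to 470 msec can enrol. They can fall in the band above 450 to 480 with no change at all.

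The question has a history in this programme. Protocol 1.3.5.2 reports a thorough QT study of 7.5 mg BID and 20 mg once daily over 5 days. At 7.5 mg the upper bound of the 90% CI for the placebo-corrected QTcF change "exceeded the 10 msec threshold at multiple time points". The protocol judges a clinically relevant effect unlikely. This trial gives 15 mg BID for 48 weeks against placebo, so its by-visit ECG data are direct randomised evidence at that dose.

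**Working it through.** **Step 1. Promise against plan.** The documents state no ECG sample size or power, so there is no figure to reproduce. The first check is textual.

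| Item | Laboratory tests (SAP 10.3.5) | Vital signs (SAP 10.3.6) | ECG (SAP 10.3.7) |
|---|---|---|---|
| Named in protocol 9.1.6.7 for changes over time | Yes | Yes | Yes |
| Value and change by visit | Yes | Yes | No |
| Baseline category counts | Yes (shift tables) | Yes (except weight) | No |
| Assessed at baseline, Weeks 4 to 48 and follow-up | Yes | Yes | Yes |

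SAP 9.2 includes a baseline rule for ECG data, so change from baseline can be computed.

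**Step 2. What the maximum-based table can show.** From the documents: about 115 patients per arm (SAP 3.1) and five post-baseline treatment visits with single ECGs (protocol 6.1.9 and Table 7). Assumed, because the documents give nothing: SD of QTcF change at one visit of 10, 15 or 20 msec; normal changes; correlation 0.5 between visits through the shared baseline. Power at two-sided 0.05 serves only as a yardstick of visibility, since neither document plans an ECG test.

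Mean change at one visit: SE = SD × √(2/115), power = Φ(shift/SE − 1.96). For a 5 msec shift:
- SD 10: SE 1.32, Φ(3.79 − 1.96) = 0.966
- SD 15: SE 1.98, Φ(2.53 − 1.96) = 0.715
- SD 20: SE 2.64, Φ(1.90 − 1.96) = 0.474

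Maximum change: the largest of five correlated changes was simulated (400,000 draws) to give the share of patients in each band. Power = Φ((|p1 − p0| − 1.96 × SE0)/SE1), with SE0 from the pooled share and SE1 from the separate shares. Example for 5 msec and SD 15: p0 = 9.6/115 = 0.083, p1 = 18.4/115 = 0.160, SE0 = 0.0431, SE1 = 0.0428, power about 0.42.

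| Shift (msec) | SD | Power, mean at one visit | Patients above 30 msec of 115, placebo vs losmapimod | Power, share above 30 | Power, share below 0 |
|---|---|---|---|---|---|
| 5 | 10 | 97% | 0.7 vs 3.0 | 22% | 74% |
| 5 | 15 | 71.5% | 9.6 vs 18.4 | 42% | 45% |
| 5 | 20 | 47% | 24.3 vs 35.0 | 37% | 30% |
| 10 | 10 | above 99.9% | 0.7 vs 9.7 | 82% | 98% |
| 10 | 15 | 99.9% | 9.7 vs 31.2 | 97% | 90% |
| 10 | 20 | 97% | 24.3 vs 47.6 | 92% | 74% |

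With no drug effect, the average maximum change in the placebo arm is already 8.2, 12.3 and 16.4 msec for the three SDs. That is the noise in the maximum.

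**Step 3. What the missing summary would give.** The 95% CI half-width for the between-arm difference at one visit is 1.96 × SE, about 2.6, 3.9 and 5.2 msec.

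**The case against.** The strongest defence is that the protocol's commitment is loose. It says by visit only where applicable, protocol 9.1.6 leaves details to the SAP, and protocol 9.1.6.1 treats frequency counts as the descriptive summary for categorical data. A by-arm table of maximum change therefore partly meets the commitment. The SAP also applies visit windows to safety data (9.5.1) and refers in general terms to by-visit summaries of continuous safety variables (10.3), so the shells may contain an ECG table.

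Part of this stands. The omission is established for the SAP text, not for the shells. But SAP 10.3.5 and 10.3.6 spell out their by-visit summaries, and a programmer following 10.3.7 as written would produce none. Unseen shells and a general sentence do not replace the specification.

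A limit on the benefit also stands. ECGs are single and locally read. They precede blood sampling, and PK sampling starts just before the dose, so the Week 4 and Week 48 ECGs appear to be predose. By-visit means would not settle the QT question alone.

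A reader might draw three stronger inferences that the documents do not support:
- *That the plan ignores baseline.* The maximum-change table compares each patient with her or his own baseline, and it partly answers the point about women enrolled at 451 to 470 msec.
- *That a QT effect would go unseen.* A shift of about 10 msec would usually show in the change table, and every ECG is listed.
- *That the thorough QT study showed prolongation beyond 10 msec.* Only the upper 90% CI bound exceeded it. No subject exceeded 480 msec or changed by 60 msec or more. Modelling at about twice the 15 mg BID exposure kept the upper bound within 10 msec and the median below 5 msec.

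**Conclusion.** The point holds as a mismatch between protocol and SAP. A descriptive summary that the protocol commits to, for a named part of the safety endpoint, has no counterpart in SAP 10.3.7, and SAP 11 does not declare the departure. This conclusion rests on the text alone.

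The consequence is moderate. It concerns small shifts, where the mean is the more sensitive summary at all three assumed SDs. At 5 msec its advantage over the share above 30 msec runs from 75 percentage points (97% against 22%, SD 10) to about 10 (47% against 37%, SD 20). Against the better of the two outer bands it is smaller: 23, about 26 and about 10 points. The variances and the correlation are assumptions, so these figures show direction and rough size only. The primary efficacy result is not affected. The change should be made, because without it a statement of no QT effect from this trial would rest on the less sensitive summaries.

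**What to change.** In SAP 10.3.7:
1. Add descriptive statistics by arm of value and change from baseline for QTcF and the other ECG intervals collected, at baseline, Weeks 4, 12, 24, 36 and 48, and safety follow-up. The wording of 10.3.5 and 10.3.6 can be reused.
2. Show baseline QTcF category counts, or a shift from baseline category to maximum on-treatment category.

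A between-arm QTcF difference with a confidence interval is optional, since the protocol promises only descriptive statistics. If the by-visit summary is deliberately left out, SAP 11 must declare and justify it. The shells should be checked to match.

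The cost is one or two standard tables from ECGs already scheduled at every one of these visits, with no new assessments.

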10.4 CLINICAL PHARMACOLOGY

10.5 PHARMACOKINETICS

Pharmacokinetics analyses are based on the pharmacokinetic analysis set.

10.5.1.1 Plasma concentrations of losmapimod

Plasma PK concentrations for losmapimod at weeks 4 and 48 at two collection times (pre-dose, and 4 hours post dose) will be summarized with the following descriptive statistics: n, mean, standard

deviation (SD), coefficient of variation (CV, %), geometric mean, geometric CV (%), median, minimum, and maximum. The number of decimal places for statistics will be as specified in Section 8.1; and CV (%) and geometric CV (%) will be displayed to 1 decimal place. Plasma concentrations will be presented graphically by collection time using boxplots. Plasma concentrations of losmapimod will be presented by patient in a listing, by FSHD type.

11. CHANGES FROM THE PROTOCOL-SPECIFIED ANALYSIS

None

APPENDIX A – LIST OF TABLES, LISTINGS AND FIGURES

See *Ph3 1821-FSH-301-FinalAnalysisShell-FINAL-v1.0.pdf*.

APPENDIX B – SCHEDULE OF ASSESSMENTS PART A: PLACEBO-CONTROLLED TREATMENT PERIOD SCHEDULE OF ASSESSMENTS

Event/Assessment	Screening	Baseline	Week 4	Week 12	Week 24	Week 36	Week 48	ET Visit ^a	Safety F/U █ after last dose of study drug	Safety F/U Phone Screen █ after last dose of study drug ^b
Visit Number	0	1	2	3	4	5	6	-	Variable ^c	Variable ^c
Study Day	█	1	28	84	168	252	336	-	343	373
Visit Window (days) ^d	N/A	±7	±7	±7	±7	±7	±7		±3	±5
Clinic visit	X	X	X	X	X	X	X	X	X	
ICF	X									
Inclusion/ exclusion	X	X								
Demographics	X									
Medical history	X									
Weight ^e	X	X			X		X	X	X	
Height ^e and BMI	X									
Genetic confirmation of FSHD ^f	X									
Randomization		X								
█ █	█									
Urine drug screen ^h	X									

REACH TRIAL

Event/Assessment	Screening	Baseline	Week 4	Week 12	Week 24	Week 36	Week 48	ET Visit ^a	Safety F/U [REDACTED] after last dose of study drug	Safety F/U Phone Screen [REDACTED] after last dose of study drug ^b
Visit Number	0	1	2	3	4	5	6	-	Variable ^c	Variable ^c
Study Day	[REDACTED]	1	28	84	168	252	336	-	343	373
Visit Window (days) ^d	N/A	±7	±7	±7	±7	±7	±7		±3	±5
Vital signs ⁱ	X	X	X	X	X	X	X	X	X	
Standard 12-lead ECG ^j	X	X	X	X	X	X	X	X	X	
Physical examination ^k	X	X	X	X	X	X	X	X	X	
Urinalysis	X	X	X	X	X	X	X	X	X	
Serum FSH ^l	X									
Serum pregnancy test ^m	X									
Urine pregnancy test ⁿ		X	X	X	X	X	X	X	X	
Hematology	X	X	X	X	X	X	X	X	X	
Biochemistry ^o	X	X	X	X	X	X	X	X	X	
Serology (HBsAg, HCV, and HIV 1/HIV 2) ^p	X									
PK ^q			X				X	X ^r		
[REDACTED]			[REDACTED]	[REDACTED]			[REDACTED]	[REDACTED]		
RWS	X	X	X	X	X	X	X	X ^r		
Hand-Held Dynamometry		X	X	X	X	X	X	X ^r		
Neuro-QoL-UE Function	X	X	X	X	X	X	X	X ^r		

REACH TRIAL

Event/Assessment	Screening	Baseline	Week 4	Week 12	Week 24	Week 36	Week 48	ET Visit ^a	Safety F/U █ after last dose of study drug	Safety F/U Phone Screen █ after last dose of study drug ^b
Visit Number	0	1	2	3	4	5	6	-	Variable ^c	Variable ^c
Study Day	█	1	28	84	168	252	336	-	343	373
Visit Window (days) ^d	N/A	±7	±7	±7	±7	±7	±7		±3	±5
MSK MRI	X				X		X	X ^r		
PGIC			X	X	X	X	X	X ^r		
█			█	█	█	█	█	█		
█			█	█	█	█	█	█		
█			█	█	█	█	█	█		
█			█		█		█	█		
█			█				█	█		
█			█				█	█		
Study drug dispensation		X	X	X	X	X				
Study drug count			X	X	X	X	X	X		
Qualitative exit interview							X			
Medications review	Continuous from signing ICF through █ safety follow-up visit									
Concomitant treatments and procedures										
Adverse events										

REACH TRIAL

Abbreviations: BMI = body mass index; ECG = electrocardiogram; [REDACTED]; ET = early termination; FSH = follicle stimulating hormone; FSHD = facioscapulohumeral muscular dystrophy; F/U = follow-up; HBsAg = hepatitis B surface antigen; HCV = hepatitis C virus; HIV = human immunodeficiency virus; ICF = informed consent form; MRI = magnetic resonance imaging; MSK = musculoskeletal; Neuro-QoL = Quality of Life in Neurological Disorders; [REDACTED] PGIC = Patient Global Impression of Change; [REDACTED]; PK = pharmacokinetics; PRO = patient-reported outcome; RWS = reachable workspace; UE = upper extremity.

- ^a If a patient prematurely discontinues study treatment, they will be encouraged to remain in the study and continue with all other aspects of the study. If a patient decides to prematurely discontinue study treatment and not continue with all other aspects of the study, they will be considered to have withdrawn from the study. If a patient withdraws from the study, they will be asked to complete an ET visit as soon as possible after the decision to terminate study participation and to complete the safety follow-up visit [REDACTED] days and a safety phone screen [REDACTED] days after their last dose of study drug. If the ET visit will be scheduled more than [REDACTED] after the last dose of study drug, the safety follow-up and ET visits may be combined, with no duplication of assessments required.
- ^b The [REDACTED] safety follow-up will be required for all patients who discontinue study treatment early or choose not to rollover into Part B. This assessment may be performed as a phone screen, unless ongoing clinical laboratory findings or AEs require additional follow-up.
- ^c Patients who do not choose to rollover into Part B only.
- ^d Scheduled visits may be split over 2 days, if required, and must be completed within the protocol-defined visit windows. Unscheduled visits may be performed if clinically indicated.
- ^e Weight and height will be measured with shoes off and preferably with the same balance at each visit.
- ^f Genetic confirmation must be obtained before the patient is randomized. Genetic confirmation can come from previous testing, if verified with appropriate documentation from an accredited laboratory. If genetic testing is necessary, the [REDACTED] screening window and activities will not start until the results are obtained and verified by the Principal Investigator.
- ^g Patients must have a Ricci score of 2 to 4 to be eligible. The score will be assigned according to the worst clinical assessment on physical examination. Patients who are wheelchair-dependent or dependent on walker or wheelchair for activities are not permitted to enroll in the study.
- ^h Urine drug screen is for drugs of abuse including cocaine, amphetamines, opiates (morphine), benzodiazepines, and cannabinoids.
- ⁱ Vital signs (pulse rate, respiration rate, blood pressure, and temperature) will be collected after the patient has been seated or recumbent for at least 5 minutes and before any 12-lead ECG assessment or blood sampling is performed.
- ^j Twelve-lead ECGs will be performed after patients have been recumbent for at least 5 minutes, after the measurement of vital signs, and before any procedures that may affect heart rate (eg, blood sampling).
- ^k Physical examination at the screening visit and safety follow-up includes an evaluation of body systems, including but not limited to the following: skin; head, eyes, ears, nose, and throat; respiratory system; cardiovascular system; abdomen (liver, spleen); lymph nodes; neurological system; and musculoskeletal system.
- ^l Serum follicle-stimulating hormone testing is required for suspected postmenopausal female patients only.
- ^m Serum pregnancy tests will be performed for all female patients of child-bearing potential at the screening visit.

REACH TRIAL

- ⁿ Urine pregnancy tests will be performed for all female patients of child-bearing potential before randomization and before dispensation of study drug at all other visits. If pregnancy is found, patients must be terminated from the study effective immediately.
- ^o For the screening visit, patients will be required to fast for at least 4 hours prior to laboratory blood samples being taken.
- ^p Subjects with a known history of hepatitis infection must be tested to confirm active infection. All subjects will be tested for hepatitis B surface antigen and, if positive, will not be allowed to enroll in the study. All subjects will be tested for hepatitis C antibody and, if positive, should be tested for viral RNA. If the viral RNA test is negative indicating inactive/resolved hepatitis C infection, then the subject can enroll in the study as long as their liver panel is within range of the inclusion and exclusion criteria. If the viral RNA test is positive, indicating active viral hepatitis C, the subject will not be allowed to enroll in the study.
- ^q Patients will be required to take their study drug dose in-clinic and blood collection for PK will occur immediately predose and 4 hours (\pm 30 minutes) after administration of the study dose.
- ^r If the ET visit occurs \geq 12 weeks after the last visit, noted assessments should be performed. If the ET visit occurs \geq 24 weeks after the last visit, MRI should be performed.

